#### ***5.2.3.2 Efficacy Population***

All randomized subjects who receive at least one dose of a study drug and who have at least three observations of PEBEQ Item 3 (event-specific bother) in the baseline period and at least one in the treatment period will be included in the modified intent-to-treat (MITT) population. The MITT population will be used for the analysis of all baseline characteristics and the analysis of all efficacy data.

#### ***5.2.3.3 Psychometric Population***

To adequately assess the reliability and validity of the PEBEQ Item 3 (event-specific bother), all eligible subjects entering the baseline period who indicate a 4 or greater on the Screening 11-point NRS Scale to Assess Bother will be included in the analyses (psychometric population). The PEBEQ Item 3 (event-specific bother) analysis set will consist of all subjects with valid sexual event data completed between screening and randomization.

The analysis of responsiveness to change and the derivation of meaningful change will be performed on the MITT population.

#### ***5.2.3.4 Safety Population***

All subjects who are treated will be included in the safety population. The safety population will be used for the analysis of all safety data.

#### ***5.2.3.5 Interim Analysis***

No interim analysis is planned for this study.

#### ***5.2.3.6 Demographics and Baseline Characteristics***

Demographic and other baseline characteristics will be summarized for each treatment group and subgroup (site, circumcision status). The number of subjects who are randomized, receive study treatment, complete treatment and withdraw from the study will be presented, along with the reasons for withdrawal.

### 5.2.3.7 Treatment Compliance

The subjects' compliance for the return of the canisters at the end of treatment will be summarized by treatment group. Compliance is calculated as  $100 \times (\text{total number of canisters returned up to the end of treatment} / \text{total number of canisters dispensed at the start of treatment})$ .

The percentage of encounters where the study medication is used will be summarized by treatment group. For encounters where the study medication is used, the percentage of encounters where the protocol-planned dose is used and the mean dose expressed as a percentage of the protocol-planned dose will also be summarized by treatment group.

### 5.2.3.8 Efficacy Analyses

The number of encounters, penetrations, ejaculations, anteportal ejaculations and penetrations without ejaculation will be summarized descriptively over the 4 weeks of treatment overall and for subgroup categories (treatment, site, circumcision status). Additionally the number of individual IELTs that are  $\leq 30$  seconds,  $>30$  seconds- $\leq 1$  minute,  $>1$  minute- $\leq 2$  minutes, and  $>2$  minutes will also be summarized descriptively over the 4 weeks of treatment.

Descriptive statistics will include sample size, number of missing observations, counts or mean values and standard deviations for discrete and continuous variables, respectively.

#### Primary objective

The primary response variable is success on the PEBEQ Item 3 (event-specific bother), where success is defined *a priori* as having a 1-point or greater improvement between the mean response over the treatment period and the mean response during the baseline period. Success will be modelled using a generalized linear mixed effects model with treatment, circumcision status and baseline mean PEBEQ Item 3 (event-specific bother) score as fixed effects and site as a random effect. The model assumes a binomial family with logit link. The null hypothesis of no treatment effect will be tested after adjustment for these other covariates in the usual manner. From this model, estimated odds ratio of PSD502 to placebo and the corresponding 95% confidence interval will be calculated. The distributional assumptions of the model will be evaluated to ensure a satisfactory fit prior to statistical estimation and testing.

Additionally, the treatment effect for each circumcision status will be evaluated by adding the treatment-by-circumcision status interaction to the above model. From this model, estimated odds ratio of PSD502 to placebo and the corresponding 95% confidence interval for each circumcision status will be calculated.

#### Secondary objectives

Secondary response variables are listed in Section 4.1.2. Secondary objectives include evaluation of the treatment effect on the secondary responses of the study, regardless of the

primary response, and also evaluation of the relationship between the primary response to each of the secondary responses. Each of these will include evaluation of circumcision and site effects. In some cases subject effects will be included, as described below.

PGI-C and PGI-C-Bother are measures of change. The median treatment effect on the PGI-C and on the PGI-C-Bother will each be computed using a non-parametric test adjusted for covariates of site and circumcision status. A linear model will be fitted with site and circumcision status as covariates.

A linear mixed effects model will be used to evaluate treatment effect on IELT during the study. The fixed effects are period (baseline or treatment period), treatment, period-by-treatment interaction and circumcision status and the random effects are site and subject within site. From this model, the mean difference between PSD502 and placebo in the change from baseline will be estimated and the corresponding 95% confidence interval calculated.

The same analysis will be conducted on PGI-S, Independent NRS Bother Item, and IEQI.

Scoring for IPE is shown in Appendix 8.7, Section 8.7.2, which results in three Domain Scores per subject. A linear mixed effects model will be used to evaluate treatment effect on the change from baseline in each of the IPE domains. The fixed effects are treatment, circumcision status and baseline, while site is the random effect. From this model, the mean difference between PSD502 and placebo in the change from baseline will be estimated and the corresponding 95% confidence interval calculated.

In each case with the secondary objectives, the distributional assumptions of the model will be evaluated to ensure a satisfactory fit prior to statistical estimation and testing.

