The placebo spray will be administered in the same manner as the PSD502 spray.

Criteria for Evaluation:

Efficacy:

The primary efficacy variable is the:

- Success on the PEBEQ Item 3 (event-specific bother), where success is defined as having a 1-point or greater improvement between the mean response over the treatment period and the mean response during the baseline period

The secondary efficacy variables are the:

- PGI-C
- PGI-S
- PGI-C-Bother
- IELT
- IEQI
- Change from baseline in the IPE Control, Distress and Satisfaction Domain Scores
- Independent NRS Bother Item

The exploratory efficacy variables are the:

- PEBEQ Multi-Item Event Specific Subscale Total

- PEBEQ Multi-Item General Subscale Total

Psychometric:

- PEBEQ Item 3 (event-specific bother)

Safety:

Safety variables include study drug exposure, the nature, incidence, relationship and severity of AEs and serious AEs (SAEs), incidence of and reasons for withdrawals, laboratory parameters, use of concomitant medications, vital signs, findings on physical examination, 12-lead ECG and visual examination of the penis.

Statistical Methods

Sample Size: In order to assess the proportion of subjects who achieve a 1-point or greater improvement over 4 weeks in the mean PEBEQ Item 3 (event-specific bother), 100 subjects will be randomized into this pilot study, 50 per arm (allowing for a 10% dropout rate). This sample size is sufficient to detect a difference of 30% in success rates when the placebo rate is 20%, with power 80% using a chi square test with a 5% Type I error rate.

In order to assess the psychometric properties of the PEBEQ Item 3 (event-specific bother), the 100 subjects will be used. This sample size is sufficient to provide estimates of meaningful change; in a validation study conducted on 56 males to test the psychometric performance of the full PEBEQ including the General and Event Specific subscales, the standard error associated with correlations of about 0.50 on a number of patient reported outcomes (PROs) was about 0.12. With a sample size of 100, the standard error is expected to decrease to around 0.05 to 0.08.

Randomization:

A randomization schedule assigning subjects to treatment will be defined for each site and stratified by circumcision status. Each schedule will be blocked, independently of the other schedules.

Analysis Populations:

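### In six period-based models circumcision enters only as a main effect, so the reported change-from-baseline contrast is not adjusted for this stratification factor

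*SAP*

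**What the plan says.** Randomization is stratified by site and circumcision status. The Protocol Synopsis (Randomization) states: "A randomization schedule assigning subjects to treatment will be defined for each site and stratified by circumcision status".

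For IELT, SAP Section 5.2.3.8 (Secondary objectives) specifies a linear mixed model: "The fixed effects are period (baseline or treatment period), treatment, period-by-treatment interaction and circumcision status"; "the random effects are site and subject within site". From it, "the mean difference between PSD502 and placebo in the change from baseline will be estimated". The model is then extended: "The same analysis will be conducted on PGI-S, Independent NRS Bother Item, and IEQI". The Exploratory objectives part of the same section uses identical terms for the two PEBEQ multi-item subscales, and the Protocol Synopsis (Efficacy Analysis) repeats all six models. None lists a circumcision-by-period term.

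Two other analyses are built differently. The IPE model takes the change score as its outcome: "The fixed effects are treatment, circumcision status and baseline, while site is the random effect". The primary model takes success, itself defined by change, and also includes circumcision status.

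On circumcision more generally, the SAP says of the secondary objectives: "Each of these will include evaluation of circumcision and site effects". The synopsis adds that treatment effects will be examined within each circumcision status, but gives no model term for doing so on these six endpoints.

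**The concern.** A reader who sees circumcision status among the fixed effects will assume that the treatment contrast is adjusted for it. In the primary and IPE models it is. In the six period models the same covariate describes only a man's average level over both periods, while the reported quantity is a difference in change.

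Two things follow if circumcision status affects how much men change. Variation in change that the factor could explain stays in the error. Any difference between arms in the share circumcised also passes directly into the estimate. In addition, the circumcision coefficient from these models says nothing about change, so it is a weak answer to the SAP's stated intention to evaluate circumcision effects on the secondary responses.

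**Working it through.** The plan gives no figure on this point. Its only planning figure is the sample size, used here just to set n: 20% versus 50%, two-sided 5%, 80% power and a continuity-corrected chi-square test give 45 per arm, and 45 / 0.9 = 50.

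**1. Algebra.** Write the planned mean as

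E[Y] = a + b·period + c·treatment + d·period·treatment + e·circumcision.

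- Baseline (period = 0): a + c·treatment + e·circumcision.
- Treatment period (period = 1): a + b + (c + d)·treatment + e·circumcision.
- Change: b + d·treatment.

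The coefficient e is gone, and the reported contrast is d. Site and subject intercepts cancel in the same way. If the outcome is the change itself, as for IPE, a circumcision term stays in the equation and does adjust d.

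**2. Numerical check.** Simulated trials: 90 men, 15 sites, 60 runs per scenario, variance components treated as known. Assumed: true effect 0.5, circumcision effect 1.0 on level and 1.0 on change.

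- Four encounters per period: the estimates with and without the circumcision main effect are identical.
- Unequal encounters (3–7 at baseline, 1–8 on treatment): they differ by 0.005 to 0.008 on average and by 0.023 at most, against a standard error near 0.11. The cancellation is then very close but not exact, because the fit uses a little between-subject information.
- Deliberately extreme imbalance (50% versus 80% circumcised by arm), equal encounters: the planned model gives 0.806, as does the model with no circumcision term. Adding circumcision-by-period gives 0.501. The shift agrees with (0.80 − 0.50) × 1.0 = 0.30.
- Circumcision balanced by arm, equal encounters: all three models give the same estimate.

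**3. Precision, one value per man per period.** Let p be the share uncircumcised (assumed 0.3) and δ the circumcision effect on change, in residual SDs of change (assumed). The share of variance that the missing term would remove is p(1−p)δ² / [1 + p(1−p)δ²], with p(1−p) = 0.21. The adjusted SE at 45 per arm is √(2/45) = 0.211. The unadjusted SE is that times √(1 + 0.21δ²).

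| δ | 0.21δ² | Variance removed | Unadjusted SE |
|---|---|---|---|
| 0.3 | 0.0189 | 1.9% | 0.213 |
| 0.5 | 0.0525 | 5.0% | 0.216 |
| 0.8 | 0.1344 | 11.8% | 0.225 |

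**4. Chance imbalance.** With 50 per arm, a gap of k uncircumcised men moves the contrast by (k/50)·δ. At δ = 0.5:

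- 19 versus 11: (8/50) × 0.5 = 0.08 SD.
- A gap of 3: (3/50) × 0.5 = 0.03 SD.

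Up to 30 sites with two circumcision groups each make up to 60 strata for 100 men, so blocking does not guarantee overall balance. Simulations of the allocation (30% uncircumcised, 10 to 30 sites, blocks of 2 or 4, all assumed) gave a mean gap of 1.8 to 3.6 men, and a gap of 8 or more in 0 to 10% of trials.

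**The case against.** The strongest reply is that this is a refinement with no consequence for validity. Much of that stands.

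- **Bias.** A reader might infer that the six treatment estimates are biased. They are not: randomization keeps them unbiased on average, and blocking within site and circumcision status limits imbalance. A 19 versus 11 split is uncommon, and the 50% versus 80% case above only shows the mechanism.
- **Size.** The 2% to 12% range is for one value per man per period. These outcomes are recorded per encounter. In a small simulation of the planned random-intercept model on encounter rows (assumed: 45 per arm, 5 encounters per period, 30% uncircumcised, 15 runs per scenario), the added term cut the model-based variance by 0.3%, 0.6% and 1.4% at 0.3, 0.5 and 0.8 SD. When men also varied in their change (SD 0.6), the cuts were 0.6%, 1.3% and 2.4%. The gain may well be small.
- **Section 5.2.2.** A reader might infer that the circumcision question posed there goes unanswered. The documents do not support this. That question concerns the success rate, and the primary analysis answers it with a circumcision covariate, a treatment-by-circumcision interaction and an odds ratio for each status.
- **Other plans.** Evaluation by circumcision status is announced in the synopsis, and the SAP's general promise on circumcision effects names no specific quantity, so a main effect meets it literally. Sections 5.2.3 and 5.2.3.12 also refer to a separate analysis plan to be finalized before database lock. These points soften the criticism, but no listed term in the six models acts on change.
- **Site.** Because the site intercept also cancels, a reader might infer that a site-by-period random effect is needed. With 100 / 30, or about three men per site if all sites enrol, that variance component would be poorly estimated. It is not required.

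What the reply does not remove is the structural point: the stratification factor is listed in the model but does not act on the reported effect.

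**Conclusion.** The point holds. In four secondary and two exploratory analyses, the change-from-baseline contrast is in effect unadjusted for circumcision status, although randomization is stratified by it and the primary and IPE models do adjust for it. The primary, PGI-C, PGI-C-Bother and IPE analyses are not affected.

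The consequence is limited to precision and residual chance imbalance, and arises only if circumcision status affects change. Its size is unknown, because the documents give neither that effect nor the share of men circumcised; every magnitude above rests on assumed values. The change is worth making before the analysis plan is finalized because it is nearly free and brings these models into line with the trial's own design.

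**What to change.** In SAP Section 5.2.3.8 (Secondary and Exploratory objectives) and the matching synopsis text:

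1. Add a circumcision-by-period fixed effect to the six models. Keep period-by-treatment as the reported contrast.
2. Report the circumcision-by-period estimate with its 95% confidence interval as the evaluation of circumcision effects on change.
3. For treatment effects by circumcision status, specify a supplementary model that adds treatment-by-circumcision (so that all two-way terms are present) and treatment-by-period-by-circumcision. Report the contrast and 95% confidence interval for each status, in parallel with the interaction model already planned for the primary endpoint. The circumcision-by-period term alone cannot show whether the treatment effect differs by status.

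The cost is a sentence or two of text, one fixed-effect degree of freedom in each main model and two more in each supplementary model. No new data are needed.

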Subjects and their sexual partners will attend a Screening Visit (Visit 1) at which they will provide written informed consent. Subjects will be asked to complete a Subject Contact Form that collects the subject's preferred contact information for Plethora's selected vendor for qualitative interviews and the subjects will be screened for eligibility. The subject will be asked to answer a screening question on how bothered they are because of the quickness of their ejaculation on an 11-point NRS scale to confirm that they are bothered and will also be asked to complete the International Index of Erectile Function 5 (IIEF-5) questionnaire in order for the Investigator to assess erectile function. Screening will involve collection of demographic information, medical history (including history of PE), medication history, physical examination including visual examination of the glans penis, heart rate (HR), blood pressure (BP), 12-lead electrocardiogram (ECG) and blood sample collection (for hematology and biochemistry). As part of the screening procedures to confirm the subject's eligibility, the subject's sexual partner will undergo a urine pregnancy test at Visit 1. This result must be negative in order for the subject to participate in the study. Subjects that pass the initial screening assessments will then undergo a baseline evaluation period of 4 weeks during which they are required to have at least three sexual encounters. They will be provided with a stopwatch to measure IELT, a diary card in which to record adverse events (AEs), concomitant medications, date and time of sexual intercourse, PEBEQ responses, PGI-S, Independent NRS bother item, IEQI and IELT data after each encounter. They will also receive an electronic date and time stamper to document the time at which they record details for each sexual encounter in the diary card. Subjects will be instructed to start timing at vaginal penetration, stop timing at the start of ejaculation and that the diary must be completed immediately after the encounter if possible or within 12 hours of the encounter.

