#### Exploratory objectives

Exploratory efficacy variables include the:

- PEBEQ Multi-Item Event Specific Subscale Total
- PEBEQ Multi-Item General Subscale Total

A linear mixed effects model will be used to evaluate treatment effect during the study. The fixed effects are period (baseline or treatment period), treatment, period-by-treatment interaction and circumcision status and the random effects are site and subject within site. From this model, the mean difference between PSD502 and placebo in the change from baseline will be estimated and the corresponding 95% confidence interval calculated.

Further analyses as suggested by the data may also be undertaken.

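### The repeated-measures models for IELT, PGI-S, NRS bother and IEQI let each arm have its own baseline mean, so some precision is lost; a common baseline mean with a subject-by-period effect would be better

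*SAP*

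**What the plan says.** SAP 5.2.3.8 (Secondary objectives) specifies a linear mixed model for IELT in which "The fixed effects are period (baseline or treatment period), treatment, period-by-treatment interaction and circumcision status". Its random part has a site term and a subject term nested in site, and nothing else. The next paragraph extends it: "The same analysis will be conducted on PGI-S, Independent NRS Bother Item, and IEQI". Under Exploratory objectives the same structure serves the two PEBEQ multi-item subscales. In each case "the mean difference between PSD502 and placebo in the change from baseline will be estimated", which is the period-by-treatment interaction.

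Two other models in the same section treat baseline differently. For the IPE domains, "The fixed effects are treatment, circumcision status and baseline, while site is the random effect". For the primary endpoint the model takes "treatment, circumcision status and baseline mean PEBEQ Item 3 (event-specific bother) score as fixed effects and site as a random effect".

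Baseline data for the four secondary outcomes exist. The Protocol synopsis (Methodology) has subjects record "PEBEQ responses, PGI-S, Independent NRS bother item, IEQI and IELT data after each encounter", over a "baseline evaluation period of 4 weeks during which they are required to have at least three sexual encounters". The synopsis (Efficacy Analysis) repeats the SAP's models. The text supplied gives no reason for the different handling of baseline and no baseline-adjusted sensitivity analysis.

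**The concern.** In a randomized trial the two arms share one expected baseline mean, and any observed difference is chance. A model with a treatment main effect estimates that difference as if it were real. The interaction then subtracts the whole of it, with a slope of 1, although the treatment-period value usually tracks baseline with a smaller slope. Chance imbalance is therefore over-corrected and enters the estimate as extra noise.

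At stake is the precision of four secondary and two exploratory treatment effects in a pilot of 50 per arm that is powered only for its primary endpoint. A second matter arises in the same sentence of the SAP. With a subject intercept as the only subject-level random effect, the model has no term for subjects who differ in how much they respond, so its reported SE can be too small.

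**Working it through.** **Inputs.** From the documents: at least 3 baseline encounters; use at least once a week for 4 weeks, so about 4 treatment encounters; 50 per arm with 10% dropout, so 50 × 0.9 = 45 per arm. The documents give no SD, ICC or baseline–treatment correlation for these outcomes, so those are assumed and shown as ranges. The plan states no precision figure for these outcomes. Its only sample-size figure (20% vs 50%, 80% power, two-sided 5%, continuity-corrected) reproduces as 45 per arm, and 45/0.9 = 50; it concerns the primary endpoint only.

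**Step 1: what the interaction estimates.** In simulated data with equal encounter counts, the planned model's interaction equalled the raw difference in mean change to about 2e-15. With unequal counts it is a weighted version of the same contrast.

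**Step 2: gain with 3 and 4 encounters for everyone.** Let b be the between-subject variance (the encounter ICC, total variance 1) and e = 1 − b. Per subject:

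- planned contrast: e(1/3 + 1/4)
- common baseline mean: b + e/4 − b²/(b + e/3)

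| ICC | Planned | Common baseline | Ratio | SE falls by |
|---|---|---|---|---|
| 0.3 | 0.408 | 0.306 | 1.33 | 13% |
| 0.5 | 0.292 | 0.250 | 1.17 | 7% |
| 0.7 | 0.175 | 0.1625 | 1.08 | 4% |

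The last column is 1 − 1/√ratio. Simulated mean SEs agree: 0.1345 to 0.1165 at ICC 0.3 and 0.1136 to 0.1053 at ICC 0.5, falls of 13% and 7%. The gain grows as the ICC falls (the formula gives a ratio of 1.75 at ICC 0.1).

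**Step 3: encounter counts that vary.** The documents set minimums only, and one treatment-period Item 3 response is enough for the MITT population. Simulations assumed 3–6 baseline and 1–8 treatment encounters, 45 per arm, random intercept. Dropping the treatment main effect still lowered the SE, by 1–9% in one set of runs. Over all scenarios run, the true SE (the spread of the estimate over simulated trials) fell by about 1–14%. An IPE-style model on one mean per subject did not help: true SE 0.120 against 0.118 for the planned model at ICC 0.3, and 0.109 against 0.102 at ICC 0.5.

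**Step 4: subjects who differ in response.** With the same varying counts and an assumed spread of response, the planned model reported an SE of 0.103, while the subject-mean analysis, whose SE picks up that spread, reported 0.178. The ratio is 0.103/0.178 = 0.58. Dropping the treatment main effect alone reported 0.097, so that change by itself does not cure the narrow interval. With a subject-by-period random effect added, the common-baseline model kept its advantage in true SE.

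**Step 5: unequal spread, as for IELT.** At subject level, with r = baseline SD / treatment SD and correlation ρ, the variance ratio of raw change to baseline-adjusted is 1 + (r − ρ)²/(1 − ρ²). Eligibility holds baseline IELT within 0–60 s, so its SD cannot exceed 30 s. If treatment-period spread is much larger, say r = 0.1 to 0.25, the ratio is 1.00 to 1.06 for ρ of 0 to 0.3, an SE difference of at most about 3%. At ρ = 0.5 it would be 1.08 to 1.21.

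**The case against.** The best defence is that the model choice is natural. IPE is completed once per period, at Visits 2 and 3, whereas the other outcomes are diary records after every encounter. A repeated-measures model uses all of them and weights subjects by how much they contribute. Difference in change is unbiased under randomization, these endpoints are secondary or exploratory, and a separate SAP is still to be finalized before database lock. All of this stands. It explains why the encounter-level model should be kept, but not why the arms need separate baseline means within it.

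Three stronger readings are tempting and are not supported.

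- A reader might infer that the IPE model should simply be copied across, as an equivalent and always better fix. It is not equivalent: it gives a subject with one encounter the same weight as a subject with many, and Step 3 shows that it can be less precise than the plan.
- A reader might infer a large loss. With equal SDs the subject-level ratio is 2/(1 + ρ), or 1.54 at ρ = 0.3 and 1.33 at ρ = 0.5, which reads as 54% or 33% more subjects. That needs equal spread in both periods and a modest correlation. Averaging 3 and 4 encounters under a random intercept already gives ρ of 0.60 at ICC 0.3 and 0.77 at ICC 0.5, and eligibility restricts baseline spread.
- A reader might infer that the planned intervals will always be too wide. Step 4 shows that the reported interval can instead be too narrow.

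**Conclusion.** The point holds as a modest, nearly free improvement. As written, six treatment effects are estimated without adjustment for baseline, although the baseline is collected and two other models in the same section use it. The planned estimates remain valid and unbiased; what is lost is precision.

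The fall in SE of roughly 1 to 14% rests on assumed ICCs, assumed encounter counts and equal residual variance in both periods. For IELT the gain is likely near zero, if treatment-period spread is much larger than baseline spread and the correlation is low. The direction of the gain is better supported than its size. That the random-intercept model can understate the SE depends on subjects differing in response, which is plausible but cannot be measured from the documents. Nothing here touches the primary analysis or the 100-subject calculation.

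**What to change.** In SAP 5.2.3.8, for IELT, PGI-S, NRS bother, IEQI and the two PEBEQ subscales:

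- Keep the encounter-level linear mixed model and its site and subject effects.
- Remove the treatment main effect, leaving period, period-by-treatment and circumcision status, so that both arms share one baseline mean. The period-by-treatment coefficient remains the reported contrast.
- Add a subject-by-period random effect, and let residual variance differ between periods.
- Do not substitute a one-row-per-subject model as if it were the same analysis.

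The Protocol synopsis (Efficacy Analysis) should be aligned, or the departure recorded. SAP 5.2.3.12 already allows changes before database lock if they are described with a rationale. The cost is wording and a small change in model code; no extra data or subjects are needed.
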